4.8 Economic Burden and/or Compensation for Subjects

4.8.1 Expenses

Subjects will have tests and procedures that are part of regular medical care (not part of the research), and the subjects or the subjects' insurance company or third party provider will be responsible for these costs, including co-payments and deductibles. The doctor and other health care providers will bill the cost of regular medical care to subjects or the subjects' health insurance company in the usual way. However, some health insurance plans will not pay the costs for people taking part in studies. Subject is to check with health plan or insurance company to find out what they will pay for. Taking part in this study may or may not cost your insurance company more than the cost of getting regular treatment. Before deciding to participate in the study, one should check with health insurance company to find out exactly what it will pay for under their policy. If the insurance does not pay for the charges of regular medical care, the sponsor will be contacted and may be able to reimburse.

Subjects will not need to pay for study drugs or tests and procedures that are done just for this research study.

If subject has any questions about insurance coverage, including any out of pocket expenses, or which laboratory or facilities you are allowed to have tests at, a financial counselor will be made available to you upon request.

4.8.2 Compensation/Incentives

Subjects will not be compensated for participation in this research study.

4.9 Risks of Harm/Potetial for Benefits to Subjects

4.9.1 Potential Risks:

Potential risks to the patient, secondary to panitumumab, include hypersensitivity reaction, rash, thrombosis, hypomagnesemia, hypocalcemia and pulmonary complications. Potential risks to the patient, secondary to talimogene laherparepvec, include fever, flu-like illness and injection site reactions. These will be monitored as detailed in the adverse events section. In terms of the individual's cancer, there is a risk of the treatment being ineffective, and by extension, the possibility of disease progression.

4.9.2 Consent Procedures:

Because of the above potential risks, informed consent must be obtained prior to commencing any research procedures. The PI shall seek such consent only under such circumstances that provide the prospective patient opportunity to consider whether or not to participate, and that minimize the possibility of coercion or undue influence. The information given to the patient or the representative shall be in a language understandable to the subject or representative. The informed consent document may not include any exculpatory language through which the subject or representative is made to waive any of the subject's legal rights or releases, or appears to release the investigator, the sponsor or the institution from liability for negligence.

4.9.3 Potential Benefits:

The benefits of participating in this study may be improvement in a patient's cancer either as a measure of disease activity or quality of life improvements.

4.9.4 Risk-Benefit Ratio:

Version Number: v10, March 23, 2023

Protocol Number: #091804

PI Name: [name]

Protocol Title: A Phase I Study of Talimogene
Laherparepvec and Panitumumab in Patients with
Locally Advanced Squamous Cell Carcinoma of the
Skin (SCCS)

43

RESERVED FOR IRB STAMP
DO NOT MODIFY THIS SPACE

RUTGERS | eIRB
APPROVED

IRB Form Version 12.18.2018

IRB ID: 102018002628

Approval Date:

4/12/2023

Expiration Date:

9/21/2023

All risks and benefits of this treatment will be discussed with the patient prior to enrollment on this study. Along these lines, the basic principles of what we are hoping to accomplish with the combination of panitumumab and talimogene laherparepvec followed by surgery will be explained. The potential risks detailed in Section 4.9.1 will be made clear as well, along with what measures are in place to minimize these risks.

Alternative treatment will also be discussed. These options include beginning standard chemotherapy if applicable, anti-EGFR monoclonal antibody monotherapy, monitoring off therapy, or enrolling in another clinical trial. Additionally, the importance of the knowledge gained through this study will be discussed with the patient.

All told, with the combination of employing proper patient selection and study termination criteria, close clinical and lab follow-up (both of the cancer as well as other relevant body systems), and the medical knowledge of panitumumab and talimogene laherparepvec (as FDA-approved medications for oncologic medical purposes in head and neck cancer, colon cancer and melanoma), we believe the potential benefits outweigh the risks of the trial.

4.10 Secondary Data – Records/Chart Reviews/Databases/Tissue Banks/etc.

N/A

4.11 Chart/Record Review Selection

In compliance with GCP guidelines, the medical records/medical notes, etc., should be clearly marked and permit easy identification of a subject's participation in the specified clinical study.

The investigator/authorized staff must record all data relating to protocol procedures, drug administration, laboratory data, safety data and efficacy ratings on the CRFs/eCRFs provided for the study. The investigator, by completing the signature log, may formally designate authority to complete CRFs/eCRFs to appropriately qualified staff. Any data management queries and items not adequately explained will be returned to the investigator by the monitor for clarification/correction. The investigator must ensure that data queries are dealt with promptly. Copies of all data changes and clarifications must be retained by the investigator and filed with the CRFs.

The investigator must, as a minimum, provide an electronic signature (e-signature) to each case report book to attest to the accuracy and completeness of all the data. If any changes are made to the eCRF after a form has been locked and electronically signed, the investigator will be required to perform an additional e-signature authorising agreement with any new information or changes to the eCRF.

All corrections on the eCRF will be automatically tracked and a reason for change is always required. In the eCRF, the audit trail function will allow the changes made to be viewed on each item entered.

If requested, the investigator will provide the sponsor, applicable regulatory agencies and applicable EC with direct access to any original source documents.

4.12 Secondary Specimen Collection

N/A

5.0 Special Considerations

5.1 Health Insurance Portability and Accountability Act (HIPAA)

N/A

Version Number: v10, March 23, 2023

Protocol Number: #091804

PI Name: [name]

Protocol Title: A Phase I Study of Talimogene
Laherparepvec and Panitumumab in Patients with
Locally Advanced Squamous Cell Carcinoma of the
Skin (SCCS)

RESERVED FOR IRB STAMP
DO NOT MODIFY THIS SPACE

RUTGERS | eIRB
APPROVED

IRB Form Version 12.18.2018

IRB ID: 1402018002628

Approval Date:

4/12/2023

Expiration Date:

9/21/2023

5.2 Family Educational Rights and Privacy Act (FERPA)

N/A

5.3 NJ Access to Medical Research Act

N/A

5.4 General Data Protection Regulation (GDPR)

N/A

5.5 Code of Federal Regulations Title 45 Part 46 (Vulnerable Populations)

N/A

6.0 Data Management Plan

6.1 Data Analysis

6.1.1 Statistical Considerations

This is a pilot feasibility study that will assess the safety and preliminary efficacy of this approach. As a phase I trial, safety of the combination will be assessed and the study stopped early for subject safety according to stopping rules defined in section 6.3.2 below. A two-stage design often used for phase II studies will be applied with the objective of estimating response rate as a measure of efficacy.

Descriptive statistics for all outcome measures and patient characteristics will be provided. The response rate of the drug will be assessed according to the decision rule based on Simon's Two-Stage Design outlined in the Sample Size Justification Section. As a secondary outcome, the pCR will be calculated and reported with its 95% confidence interval. The estimation of progression-free survival (PFS) and overall survival (OS) will be performed by the Kaplan-Meier product limit method. Logrank test and Cox proportional hazards model will be used to explore the associations between outcome measures (PFS and OS) and patient characteristics.

6.1.2 Interim Safety Assessment and Stopping rules

We will employ a 3 + 3 study design in the first six patients enrolled. This will allow for early detection of unexpected safety signals and will allow for rapid implementation of measures to diminish the risk of toxicity to subsequently enrolled subjects. The interim safety assessment will start and includes the rules of the 3+3 design based on the incidence of DLTs. We plan to continue monitoring the treatment safety after the first 6 patients are recruited. Monitoring will continue after every subsequent patient. The stopping rule will be determined by the posterior probability of the event rate of the either hospitalizations or delays/cancellation in planned surgery, due to treatment related toxicities. Specifically, the early stopping will be triggered when the posterior probability that more than 40% patients are either hospitalized or delayed/ cancelled in surgery due to treatment related toxicities is greater than 90%. Assuming a non-informative prior, we calculated the posterior probability of toxicity related event rate of 40% given that k events are observed out of the first n patients, using the beta distribution with shape parameter 1+k and scale parameter 1+n-k. Table 10 highlights the posterior probability that more than 40% patients are either hospitalized or delayed/Cancelled in surgery due to treatment related toxicities being greater than 90%. If 6 or more toxicity related events that meet these criteria of resulting in hospitalization or delays/cancellation of planned surgery out of the first 10 patients are observed, the trial will be stopped.

Note that each cell of Table 11 contains the posterior probability that the true toxicity related event rate is greater than 40% given that k events are observed out of the first n patients. The prior distribution will be updated based on the number of events observed at each monitoring, and thus resulting posterior

Version Number: v10, March 23, 2023

Protocol Number: #091804

PI Name: [name]

Protocol Title: A Phase I Study of Talimogene

Laherparepvec and Panitumumab in Patients with
Locally Advanced Squamous Cell Carcinoma of the
Skin (SCCS)

45

RESERVED FOR IRB STAMP
DO NOT MODIFY THIS SPACE

RUTGERS | eIRB
APPROVED

IRB Form Version 12.18.2018

IRB ID:

Approval Date:

4/12/2023

Expiration Date:

9/21/2023

probability of the event rate greater than 40% will also be updated. The study PI ([name]) then will contact the Biometrics division at the Rutgers Cancer Institute of New Jersey to obtain the updated stopping rule after each scheduled monitoring.

Table 11. Posterior probability of toxicity related event rate of 40% given that k events are observed out of the first n patients																	
	3	4	5	6	7	8	9	10	11	12	13	14	15	16	17	18	19
5	0.821	0.959	0.996	1.000	1.000	1.000	1.000	1.000	1.000	1.000	1.000	1.000	1.000	1.000	1.000	1.000	1.000
6	0.710	0.904	0.981	0.998	1.000	1.000	1.000	1.000	1.000	1.000	1.000	1.000	1.000	1.000	1.000	1.000	1.000
7	0.594	0.826	0.950	0.991	0.999	1.000	1.000	1.000	1.000	1.000	1.000	1.000	1.000	1.000	1.000	1.000	1.000
8	0.483	0.733	0.901	0.975	0.996	1.000	1.000	1.000	1.000	1.000	1.000	1.000	1.000	1.000	1.000	1.000	1.000
9	0.382	0.633	0.834	0.945	0.988	0.998	1.000	1.000	1.000	1.000	1.000	1.000	1.000	1.000	1.000	1.000	1.000
10	0.296	0.533	0.753	0.901	0.971	0.994	0.999	1.000	1.000	1.000	1.000	1.000	1.000	1.000	1.000	1.000	1.000
11	0.225	0.438	0.665	0.842	0.943	0.985	0.997	1.000	1.000	1.000	1.000	1.000	1.000	1.000	1.000	1.000	1.000
12	0.169	0.353	0.574	0.771	0.902	0.968	0.992	0.999	1.000	1.000	1.000	1.000	1.000	1.000	1.000	1.000	1.000
13	0.124	0.279	0.486	0.692	0.850	0.942	0.982	0.996	0.999	1.000	1.000	1.000	1.000	1.000	1.000	1.000	1.000
14	0.091	0.217	0.403	0.610	0.787	0.905	0.966	0.991	0.998	1.000	1.000	1.000	1.000	1.000	1.000	1.000	1.000
15	0.065	0.167	0.329	0.527	0.716	0.858	0.942	0.981	0.995	0.999	1.000	1.000	1.000	1.000	1.000	1.000	1.000
16	0.046	0.126	0.264	0.448	0.641	0.801	0.908	0.965	0.989	0.997	1.000	1.000	1.000	1.000	1.000	1.000	1.000
17	0.033	0.094	0.209	0.374	0.563	0.737	0.865	0.942	0.980	0.994	0.999	1.000	1.000	1.000	1.000	1.000	1.000
18	0.023	0.070	0.163	0.308	0.488	0.667	0.814	0.912	0.965	0.988	0.997	0.999	1.000	1.000	1.000	1.000	1.000
19	0.016	0.051	0.126	0.250	0.416	0.596	0.755	0.872	0.943	0.979	0.994	0.998	1.000	1.000	1.000	1.000	1.000
20	0.011	0.037	0.096	0.200	0.350	0.524	0.691	0.826	0.915	0.965	0.988	0.996	0.999	1.000	1.000	1.000	1.000
21	0.008	0.027	0.072	0.158	0.290	0.454	0.624	0.772	0.879	0.945	0.979	0.993	0.998	1.000	1.000	1.000	1.000
22	0.005	0.019	0.054	0.124	0.237	0.388	0.556	0.713	0.836	0.919	0.965	0.987	0.996	0.999	1.000	1.000	1.000
23	0.004	0.013	0.040	0.096	0.192	0.328	0.489	0.650	0.787	0.886	0.947	0.978	0.992	0.998	0.999	1.000	1.000
24	0.002	0.009	0.029	0.074	0.154	0.274	0.425	0.586	0.732	0.846	0.922	0.966	0.987	0.996	0.999	1.000	1.000
25	0.002	0.007	0.021	0.056	0.122	0.226	0.364	0.521	0.674	0.801	0.892	0.948	0.978	0.992	0.998	0.999	1.000
26	0.001	0.005	0.015	0.042	0.095	0.184	0.309	0.458	0.613	0.750	0.855	0.926	0.966	0.987	0.995	0.999	1.000
27	0.001	0.003	0.011	0.031	0.074	0.148	0.259	0.399	0.551	0.695	0.813	0.898	0.950	0.978	0.992	0.997	0.999
28	0.000	0.002	0.008	0.023	0.057	0.119	0.215	0.343	0.490	0.637	0.766	0.864	0.929	0.967	0.987	0.995	0.998
29	0.000	0.002	0.006	0.017	0.044	0.094	0.176	0.291	0.431	0.578	0.715	0.825	0.903	0.952	0.979	0.992	0.997

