1.5 Sample Size Justification

The combination of panitumumab and talimogene laherparepvec will be considered of no interest for further evaluation if the response rate in advanced SCCS is 25% (p_0) or less, and considered an improved treatment if the response rate in advanced SCCS is 47% (p_1) or higher. Denote the true response rate by p . Using the Simon's two-stage design [43], we will test $H_0: p \leq p_0$ vs. $H_1: p > p_1$ with 80% power and alpha=5% (one-sided). In the first stage, 13 patients will be accrued. If there are 3 or fewer responses in these 13 patients, we will terminate the study and reject the drug (combination of panitumumab and talimogene laherparepvec). Otherwise, 17 additional patients will be accrued for **a total of 30 patients**. If 12 or more responses are observed in 30 patients, the null hypothesis will be rejected and we will conclude the success of the drug.

The combination therapy approach would be considered to have limited safety if unanticipated toxicity from talimogene laherparepvec is observed. If the proportion of talimogene-laherparepvec related grade ≥ 3 toxicities that result in hospitalization or delays/cancellation of planned surgery is less than 30% of the subjects accrued, then the study accrual may continue. These toxicities do not include fever or injection site reaction which are known side effects of talimogene laherparepvec. The toxicity will be independently monitored by the Human Research Oversight Committee which will communicate any safety concerns directly to all participating Investigators.

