In one study [44], dermatologic toxicities occurred in 90% of patients and were severe (grade 3 and higher) in 15% of patients receiving panitumumab. The clinical manifestations included, but were not limited to acneiform dermatitis, pruritus, erythema, rash, skin exfoliation, paronychia, dry skin, and fissures. Monitor patients who develop dermatologic or soft tissue toxicities while receiving panitumumab for the development of inflammatory or infectious sequelae. Withhold or discontinue panitumumab for dermatologic or soft tissue toxicity associated with severe or life-threatening inflammatory or infectious complications. Patients should be advised to avoid sun exposure while receiving panitumumab.

In previous reports, the Common Terminology Criteria for Adverse Events (CTCAE) 4.0 (Table 7) have been used for EGFR-associated rash.

4) Interstitial Lung Disease (ILD)

ILD may be acute in onset and has been observed in 1.3 % of patients, and some cases have been fatal. If patients experience worsening of respiratory symptoms such as dyspnea, cough and fever, panitumumab should be interrupted and the patient should be promptly investigated. If ILD is confirmed, panitumumab should be discontinued and the patient treated appropriately.

5) Electrolyte Abnormalities

Progressively decreasing serum magnesium levels leading to severe (grade 3-4) hypomagnesemia occurred in up to 7% [45] of patients across clinical trials. Monitor patients for hypomagnesemia and hypocalcemia prior to initiating treatment with panitumumab, periodically during treatment, and for up to 8 weeks after the completion of treatment. Other electrolyte disturbances, including hypokalemia, have also been observed. Replete magnesium and other electrolytes as appropriate.

6) Infusion Reactions

In one study [44], 4% of patients receiving panitumumab experienced infusion reactions, and 1% of patients experienced severe infusion reactions (grade 3-4). Infusion reactions, manifesting as fevers, chills, dyspnea, bronchospasm, and hypotension, can occur following panitumumab administration. Table 9 and 10 show the grading criteria for infusion reactions and dose modifications for infusion reactions, respectively. Fatal infusion reactions occurred in post-marketing experience.

Table 9. Grading Infusion Reactions:

	Grade 1	Grade 2	Grade 3	Grade 4

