Once the infusion rate has been decreased due to an infusion reaction, it will remain decreased for all subsequent infusions. If the subject has a second infusion reaction at the slower infusion rate, the subject should receive no further panitumumab treatment.

Panitumumab will be immediately and permanently discontinued for serious infusion reactions that are life threatening and/or require hospitalization.

7) Photosensitivity

Exposure to sunlight can exacerbate dermatologic toxicity. Advise patients to wear sunscreen and hats and limit sun exposure while receiving panitumumab.

8) Ocular Toxicities

Keratitis and ulcerative keratitis, both known risk factors for corneal perforation, have been reported with panitumumab. Monitor for evidence of keratitis or ulcerative keratitis. Interrupt or discontinue panitumumab for acute or worsening keratitis.

9) Other Toxicities

Life-threatening and fatal infectious complications including necrotizing fasciitis, abscesses, and sepsis have been observed in patients treated with panitumumab.

Life-threatening and fatal bullous mucocutaneous disease with blisters, erosions, and skin sloughing has also been observed in patients treated with panitumumab.

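### After the 3+3 run-in, neither trial-level toxicity rule lists treatment-related death, so a death without admission and before surgery is planned counts as a non-event.

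*Combined protocol and SAP*

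**What the plan says.** Section 6.1.2 applies a 3+3 design, based on dose-limiting toxicities, to the first six patients. Section 1.7.9 defines these as grade 3 or higher events within four weeks, with listed exceptions. That definition covers a fatal event in the window.

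After that, safety is reviewed after every patient. The quantity monitored is "the event rate of the either hospitalizations or delays/cancellation in planned surgery, due to treatment related toxicities". The trial stops when the posterior probability that this rate exceeds 40% is above 90%. The posterior is computed "using the beta distribution with shape parameter 1+k and scale parameter 1+n-k", and Table 11 tabulates it. The worked boundary begins "If 6 or more toxicity related events that meet these criteria of resulting in hospitalization or delays/cancellation of planned surgery" and is set at the first 10 patients. Section 1.7.2.2 gives the same event and trigger.

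A second rule, in Sections 1.5 and 6.1.3.2, lets accrual continue if the proportion of talimogene-related grade 3 or higher "toxicities that result in hospitalization or delays/cancellation of planned surgery is less than 30% of the subjects accrued". Fever and injection site reactions are excluded.

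Death appears elsewhere. The definition of a serious adverse event (6.1.6) lists it separately from inpatient hospitalization. Section 6.1.5.1 requires notice to the IRB within 24 hours, and 6.1.5.2 covers notice to the FDA. No stop or accrual hold is attached to either. Sections 1.7.2.2 and 6.1.1 point to Section 6.3.2 for the stopping rules, but Section 6.3 as supplied has no such subsection.

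**The concern.** Safety is the first primary objective, and the protocol itself names fatal toxicities. On panitumumab, Section 1.7.6.3 says "Fatal infusion reactions occurred in post-marketing experience" and "Life-threatening and fatal infectious complications including necrotizing fasciitis, abscesses, and sepsis have been observed in patients treated with panitumumab". It also says that about 90% of severe infusion reactions came with the first infusion, which here is day 22.

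Surgery does not fill the gap for every patient. It depends on adequate response (1.1) and is first evaluated at about day 64 (1.3). Eligibility includes disease for which curative surgery would be difficult or impossible (4.1). A patient can therefore die of toxicity with no admission and no operation yet planned. The rule as written scores that patient like one with no toxicity, and the computed case for stopping becomes weaker.

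**Working it through.** **Inputs.** Event definition, 40% and 90% thresholds, and posterior: Section 6.1.2. Tabulated probabilities: Table 11. 30% condition: Section 1.5. Assumed, because the documents give no figures: a counted-event rate of 30%, and rates of uncounted deaths of 1% and 5%.

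**1. Reproduce the plan's figure.** For k events in n patients the posterior is Beta(1+k, 1+n−k), so P(rate > 0.4) = P(Binomial(n+1, 0.4) ≤ k).

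- n = 10, k = 6: P(Binomial(11, 0.4) ≤ 6) = 0.9006. Table 11 gives 0.901, the stated boundary.
- n = 10, k = 5: P(Binomial(11, 0.4) ≤ 5) = 0.7535. Table 11 gives 0.753.

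**2. Effect of one uncounted death.** Take 5 counted events in 9 patients: Table 11 gives 0.834. The tenth patient dies of treatment-related toxicity, not admitted and with no surgery planned.

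| Scoring of the death | k | n | Posterior | Decision |
|---|---|---|---|---|
| As written | 5 | 10 | 0.753 | continue |
| Counted | 6 | 10 | 0.901 | stop |

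As written, the death moves the posterior down from 0.834 to 0.753.

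**3. What the example needs.** Two other rules could act first.

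- *30% condition.* Accrual may continue only below 30%, which in 10 patients means at most 2 qualifying events. So at least 5 − 2 = 3 of the 5 events must fall outside that condition, for example because they are related to panitumumab only or are below grade 3.
- *3+3.* Patients 7 to 10 include the death and so hold at most 3 of the 5 events. At least 2 therefore occurred in the first six patients, and they must not have halted the run-in. The protocol does not state the 3+3 thresholds.

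**4. Size over the whole trial.** Let b(n) be the smallest k with posterior above 0.90: 4 of 6, 5 of 8, 6 of 10, 8 of 14, 11 of 20, 15 of 29. Let f(n, k) be the probability that the trial is still running after n patients with k events, at event rate q:

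f(n, k) = (1 − q) f(n−1, k) + q f(n−1, k−1).

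After each patient from n = 6 to 29, any mass with k ≥ b(n) is moved to stopped. Uncounted deaths are taken to occur in patients with no counted event, so the rates add when deaths are counted. This covers the Bayesian rule alone.

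| Uncounted deaths (assumed) | q as written | P(stop) as written | q with deaths counted | P(stop) with deaths counted |
|---|---|---|---|---|
| 1% | 0.30 | 0.117 | 0.31 | 0.133 |
| 5% | 0.30 | 0.117 | 0.35 | 0.215 |

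**The case against.** The strongest case against runs as follows. A fatal toxicity often involves an admission, which counts. Because treatment is framed as preoperative and every patient is to be evaluated for surgery, a death could be read as cancelling that surgery. The uncounted deaths should also be rare: Section 1.7.6.3 gives 1% for severe infusion reactions and 1.3% for interstitial lung disease, and only some of those are fatal. A composite rate rule with a 40% threshold is a blunt tool for rare deaths in any case. IRB and FDA notification, and independent monitoring by the Human Research Oversight Committee under the Data and Safety Monitoring Plan, could halt the trial.

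Much of this stands and limits the size of the point. At a 1% rate the change in stopping probability is small. The monitoring plan is not supplied, so a halting rule in it cannot be excluded.

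It does not remove the gap. The protocol does not define planned surgery, and an evaluation that has not yet taken place is not clearly an operation that was planned. The notification routes state no criterion for stopping, and the committee is given no criterion for deaths.

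A reader might infer that any treatment-related death is scored as safe, or that the trial is unprotected against deaths. The documents support neither: deaths in the run-in window meet the dose-limiting toxicity definition, deaths after admission meet the Bayesian definition, and ad hoc oversight remains.

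**Conclusion.** The point holds in a limited form. After the first six patients, neither stated toxicity rule lists treatment-related death, and one that occurs without admission and before surgery is planned lowers the Bayesian posterior. One such death can reverse the decision at n = 10, under the conditions in step 3 of the working.

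Over the whole trial, with a 30% counted-event rate, the gain from counting these deaths is 0.133 − 0.117 = 0.016 at a 1% death rate and 0.215 − 0.117 = 0.098 at 5%. All three rates are assumptions. A reader might conclude that the rule fails its purpose altogether, but the figures do not support that. It is a definitional gap in a primary safety rule. It should be closed because doing so is cheap, not because the expected effect is large.

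**What to change.** - **Sections 1.7.2.2 and 6.1.2:** define the event as a patient with treatment-related death, or with admission to hospital or a delayed or cancelled planned operation due to treatment-related toxicity.
- **Sections 1.5 and 6.1.3.2:** add only death to the listed outcomes. Keep the talimogene attribution, the grade 3 or higher limit and the exclusion of fever and injection site reactions. Carrying over the Bayesian definition would remove those limits and make this a different, broader rule.

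The cost is a short wording change in four places. Every cell and boundary of Table 11 stays as it is; only the count k can change. The downside is that the rules may fire somewhat earlier.

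The change gives a death the same weight as one hospitalization: 5 deaths in 10 patients and no other event would still give 0.753 and continue under the Bayesian rule. Whether a separate trial-level rule for deaths is also needed is for the sponsor to decide.
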